6.0 BACKGROUND DRUG INFORMATION

6.1 Tacrolimus (Prograf)

TACROLIMUS is a macrolide compound with potent immunosuppressant properties.

DOSING INFORMATION: TACROLIMUS is usually given intravenously initially in doses of 0.03 mg/kg/day for 3 days, followed by conversion to oral therapy (0.09 mg/kg twice daily); dose adjustments are required in patients with hepatic dysfunction.

HUMAN PHARMACOLOGY: The oral absorption of TACROLIMUS is erratic and incomplete; absolute bioavailability is approximately 25%; peak serum levels are seen 1 to 4 h after an oral dose, and therapeutic serum concentrations have ranged from 0.2 to 6 ng/mL; TACROLIMUS is extensively metabolized in the liver, with only small amounts of unchanged drug (2% or less) being recovered in the urine; the elimination half-life of TACROLIMUS is approximately 10 h.

CAUTIONS: Common adverse effects of TACROLIMUS are headache, hyperesthesia, tremors, circumoral numbness, insomnia, nausea, abdominal discomfort, and appetite insomnia, nausea, abdominal discomfort, and appetite changes; all of these effects occur primarily with IV TACROLIMUS and are more frequent during combined use of TACROLIMUS and CYCLOSPORINE; other adverse effects include nephrotoxicity, hyperkalemia, hyperuricemia, hyperglycemia, dysphasia, photophobia, flushing, and lymphoproliferative disorder; unlike CYCLOSPORINE, hirsutism, gingival hyperplasia, and hypertension are generally not seen with TACROLIMUS; combined therapy with CYCLOSPORINE has resulted in increases in cyclosporine serum levels and more severe nephrotoxicity.

6.2 Busulfan

BUSULFAN is an alkylating agent that interferes with DNA replication and transcription of RNA and ultimately results in the disruption of nucleic acid function.

DOSING INFORMATION: In transplantation, doses of 1 mg/kg PO are repeated to a usual cumulative dose of 16 mg/kg. The usual dose for IV Busulfan is 80% of the equivalent PO dose.

HUMAN PHARMACOLOGY: Busulfan is rapidly absorbed from the gastrointestinal tract, and measurable blood levels are obtained within 0.5-2 hours after oral administration. Within 3 minutes after IV administration in rats, 90% of the drug disappears from the blood; similar rapid decreases in blood concentrations have been reported in man. Busulfan is reported to be extensively metabolized; 12 metabolites have been isolated, but most have not been identified. The drug is slowly excreted in the urine, chiefly as methanesulfonic acid. Ten to 50% of a dose is excreted as metabolites within 24 hours.

CAUTIONS : Dose limiting toxicity is hematological. Long term therapy has been associated with pulmonary fibrosis and an Addison's like syndrome. Seizures have been reported after high dose Busulfan used for transplantation. Dilantin is often administered preventively.

6.3 Fludarabine

Fludarabine is the 2-fluoro, 5-phosphate derivative of vidarabine.

DOSING INFORMATION: Doses of 25 mg/m²/day (30-minute infusion) for 5 days every 4 weeks has been effective previously treated patients with chronic lymphocytic leukemia; in non-Hodgkin's lymphoma, a loading dose of 20 mg/m² intravenously followed by a continuous intravenous infusion of 30 mg/m²/24 hours for 48 hours, has been effective; dose reductions are suggested in renal insufficiency.

PHARMACOKINETICS: Following intravenous administration, fludarabine phosphate is rapidly dephosphorylated to 2-fluoro-vidarabine, which subsequently enters tumor cells and is phosphorylated to the active triphosphate derivative; peak plasma levels of 2-fluoro-vidarabine have ranged from 0.3 to 0.9 mcg/mL following a short infusion of 25 mg/m² fludarabine; 24% of a dose of fludarabine is recovered in the urine as 2-fluoro-vidarabine; the elimination half-life of 2-fluoro-vidarabine is 9 hours.

CAUTIONS: Myelosuppression, particularly neutropenia, is the predominant adverse effect; a severe neurotoxicity has been observed, mainly with higher doses; other adverse effects include nausea, vomiting, diarrhea, stomatitis, skin rash, and somnolence; pneumonitis has been reported in 1 patient.

CLINICAL APPLICATIONS: Intravenous fludarabine has been highly effective in heavily pretreated patients with chronic lymphocytic leukemia; the drug has also produced responses in patients with non-Hodgkin's lymphoma and acute leukemia; however, neurotoxicity has been a major concern, even with low doses, and more studies are needed to clarify its ultimate place in therapy.

6.4 CAMPATH- 1H (Alemtuzumab)

CAMPATH-1H is a humanized monoclonal antibody directed against CD52, an epitope that is abundantly expressed on T- and B- lymphocytes, but not on NK cells. It has been extensively used for the prevention of GVHD both in vitro and in vivo.

DOSING INFORMATION: In transplantation, daily doses of 20 mg are repeated for up to five times.

HUMAN PHARMACOLOGY: Campath is extensively bound to circulating CD52 in the serum as well as present in unbound form. The half life of Campath is prolonged and free Campath can be detected for several weeks after administration. Campath is usually administered intravenously, but recent data indicate that subcutaneous administration is associated with a decreased incidence of severe reactions. In some studies Campath has been admixed with the stem cell infusate.

CAUTIONS: The infusion of Campath H1 has been associated with fever, nausea, headache, vomiting, rash, chills and rigor. Occasionally hypotension and bronchospasm have been reported. This can be managed by adequate premedication.

7.0 PATIENT ELIGIBILITY

7.1 Patients with the following diseases:

Diagnosis:

Phase I portion:

- Relapsed or refractory acute myelogenous or lymphoid leukemia.
- Chronic myelogenous leukemia in accelerated phase or blast-crisis.
- Recurrent or refractory malignant lymphoma or Hodgkin's disease
- Recurrent or refractory multiple myeloma.
- Chronic lymphocytic leukemia, relapsed or with poor prognostic features.
- Myeloproliferative disorder (polycythemia vera, myelofibrosis) with transformation
- Myelodysplastic syndromes with more than 5% blasts.

Phase II portion:

- AML with active disease or beyond CR2
- MDS with more than 5% blasts

- 7.2 Zubrod performance status ≤ 2**
- 7.3 Life expectancy is not severely limited by concomitant illness.**
- 7.4 Adequate cardiac and pulmonary function. Patients with decreased LVEF or PFTS will be evaluated by cardiology or pulmonary prior to enrollment on this protocol.**
- 7.5 Calculated creatinine clearance $>50 \text{ ml/min}$.**
- 7.6 Serum bilirubin $\leq 2.0 \text{ mg/dl}$, SGPT $<3 \times \text{upper limit of normal}$**
- 7.7 No evidence of chronic active hepatitis or cirrhosis.**
- 7.8 HIV-negative**
- 7.9 Patient is not pregnant**
- 7.10 Patient or guardian able to sign informed consent.**

8.0 DONOR SELECTION, STEM CELL SOURCE AND TREATMENT PLAN.

8.1 DONOR SELECTION

When possible, an HLA compatible sibling will be used as a donor. For patients who do not have an HLA-compatible sibling, an unrelated donor will be identified.

In case of unrelated donor transplantation, high resolution DNA-based HLA typing will always be performed for HLA A, B, C and DR antigens

8.2 HEMATOPOIETIC STEM CELL SOURCE

Donor stem cells will be the preferred source of HSC in all cases. Based on donor's preference, bone marrow stem cells may be utilized in some recipients.

9.0 TREATMENT PLAN

9.1.1 All patients shall be registered with the Data Management Office.

Complete all sections of the Registration Form located on the University of Chicago Cancer Research Center web site at <http://www-uccrc.uchicago.edu/> and send the completed form by facsimile to [contact].

9.1.2 Conditioning regimen

Day	Clonazepam	Fludarabine	Busulfan	Bu pharmacokinetics	Campath
Test Dose					
-	PO				
-	PO		0.5 mg/kg	x 6	
-	PO				
Treatment Doses					
-7 PO		25 mg/m ²			20 mg
-6	PO	25 mg/m ²	AUC based	x 5	20 mg
-5	PO	25 mg/m ²	AUC based		20 mg
-4	PO	25 mg/m ²	AUC based	(x 5*)	20 mg
-3	PO	25 mg/m ²	AUC based	x 5*	20 mg
-2	PO				
-1					
0					

Comments:

Busulfan administration has been associated with a low incidence of seizures and dilantin is routinely used for seizure prophylaxis. Dilantin use is discouraged in this protocol because exposure to dilantin can affect Busulfan metabolism.⁵⁷

We recommend benzodiazepines e.g clonazepam (klonopin ®) 1 mg PO TID

Scheduling:

Busulfan test dose:

The test dose can be scheduled any day within 8 days prior to admission. Clonazepam will be started with an evening dose, the day prior to the test dose and two doses one day after test dose. Busulfan test-dose will be based on actual body weight and will be accompanied by extensive pharmacokinetic studies. This dose will be given as an outpatient.

Patients will be admitted in the evening of day -8, to start fludarabine on day -7

Fludarabine:

Fludarabine dosing will be based on actual body weight. Fludarabine will be infused over 30 minutes before busulfan treatment dose.

Busulfan treatment doses:

On each day of treatment, busulfan will be administered through a fresh infusion line at a steady rate over 3 hours. Infusion will start in the morning around 5 AM and will be completed around 8 AM, allowing ample time for pharmacokinetic sampling in the afternoon.

*Pharmacokinetic studies will be performed on the day 1 dose and again on the day 4 dose. For logistical reasons (week-end, holidays), day 3 pharmacokinetics may be performed instead of day 4. Busulfan doses may be further adjusted based on levels obtained with treatment dose 1.

Campath

All patients will receive premedication for Campath as per current standards at the UC transplant unit.

9.1.3 Dose schedule (see also statistical plan)

The targeted daily AUC of busulfan will be determined using the modified continual reassessment method.

Target AUC's are the following:

Dose level 0: 4800 mcgr.min/L.dose

Dose level 1: 5800 mcgr.min/L.dose

Dose level 2: 6800 mcgr.min/L.dose

Dose level 3: 7800 mcgr.min/L.dose

Dose level 4: 8800 mcgr.min/L.dose

Dose level 5: 9800 mcgr.min/L.dose

We do not anticipate further dose-escalation beyond dose level 5. If such dose-escalation were to be considered, we would submit an amended protocol to the IRB.

9.1.4 Bone marrow/stem cell infusion

On day 0 the stem cell product will be infused according to BMT unit policy.

Bone marrow, PBSC will not be further processed except in the case of ABO-incompatibility. In such instances, red blood cells will be removed from bone marrow products or from PBSC products containing excessive amounts of RBC (as per transplant policy).

All stem cell products procured through the NMDP will be done so in strict compliance with the protocols, policies, and procedures established by the NMDP.

9.1.5 GVHD prophylaxis

Tacrolimus 0.03 mg/kg/day IV CI over 24 hr from 4 PM day -2 until engraftment or when patient is able to take PO, then tacrolimus 0.09 mg/kg PO in 2 divided doses.

Tacrolimus should be given at full dose to maintain levels of 5-15 ng/mL through day 100. Thereafter tacrolimus will be tapered by 20% every week unless the patient has developed GVHD. In recipients of mismatched or unrelated donor transplants, tacrolimus will be continued until day 180. Thereafter tacrolimus will be tapered by 20% every week unless the patient has developed GVHD.

9.1.6 Supportive care:

Infection prophylaxis and supportive care will be as BMT unit policy. No routine growth factor support will be administered. Growth factor support will be considered in case of delayed engraftment (ANC < $0.5 \times 10^9/L$ on day 12)

9.1.7 Back-up bone marrow harvest (only for recipients of mismatched or unrelated donor transplants)

For patients transplanted in remission, a backup bone marrow or peripheral blood stem cell collection will be considered within two weeks prior to hospital admission as long as the overall marrow cellularity is greater than 30%. All backup harvests will be cryopreserved after processing for buffy coat without any further manipulation. The backup stem cells will be given if deemed clinically necessary in the event of failure to engraft by day +35, graft rejection after day +35, or graft failure after day +35.

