APPENDIX A: TREATMENT SCHEME
APPENDIX B: GVHD CRITERIA

Version 08/11/06, 09/13/2011, 02/20/2013

Principal Investigator

[name]

CO-INVESTIGATORS

[name].

[name].

[name].

[name].

[name].

[name]., Ph.D

[name].

[name].

[name].

[name].

[name]., Ph.D.

[name]., Ph.D.

[name].

University of Illinois at Chicago

Principal Investigator:

[name]

PROTOCOL ABSTRACT

Protocol:

A phase I-II study of busulfan-fludarabine conditioning and T-cell depleted allogeneic stem cell transplantation for patients with advanced hematologic malignancies

Principal Investigator:

[name].

Patient Eligibility:

Diagnosis:

Phase I portion:

- Relapsed or refractory acute myelogenous or lymphoid leukemia.
- Chronic myelogenous leukemia in accelerated phase or blast-crisis.
- Recurrent or refractory malignant lymphoma or Hodgkin's disease
- Recurrent or refractory multiple myeloma.
- Chronic lymphocytic leukemia, relapsed or with poor prognostic features.
- Myeloproliferative disorder (polycythemia vera, myelofibrosis) with transformation
- Myelodysplastic syndromes with more than 5% blasts.

Phase II portion:

- AML with active disease or beyond CR2
- MDS with more than 5% blasts

Zubrod performance status 2 (See Appendix B).

Life expectancy is not severely limited by concomitant illness.

Adequate cardiac and pulmonary function. Patients with decreased LVEF or PFTS will be evaluated by cardiology or pulmonary prior to enrollment on this protocol.

Calculated creatinine clearance >50 ml/min.

Serum bilirubin 2.0 mg/dl, SGPT <3 x upper limit of normal

No evidence of chronic active hepatitis or cirrhosis. HIV-negative Patient is not pregnant Patient or guardian able to sign informed consent.

Matched sibling donor, 1 Antigen mismatched relative or matched unrelated donor.

Treatment Plan:

See appendix A

PATIENT EVALUATION:

See section 6 and section 7

Miscellaneous Information:

Objectives:

1. To establish the maximally tolerated dose (MTD) of intravenous busulfan (Busulfan®) in combination with fludarabine as conditioning regimen for transplantation with in-vivo T-cell depletion
2. To evaluate disease free and overall survival after this conditioning regimen in patients with advanced AML and MDS.
3. To evaluate potential pharmacogenomic determinants of toxicity of this regimen.
4. To evaluate potential pharmacogenomic determinants of efficacy of this regimen.

Statistics:

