5.4 Donor type

The outcome of allogeneic transplantation is determined to a large degree by the choice of stem cell donor. The best outcomes are obtained with the use of syngeneic donors (i.e. identical twins). Grafts from such donors are accepted without risk for graft failure or graft versus host disease.

Among siblings, the probability of being identical for all major histocompatibility (HLA) antigens is approximately 25%. Allogeneic matched (HLA-identical) siblings can be identified for approximately 20-30% of the population. Seventy percent of patients who might otherwise benefit from allogeneic hematopoietic stem cell transplantation lack a suitably matched related donor. Alternative donor sources include partially matched related donors, unrelated volunteers, and previously banked placental blood. Recipients of unrelated donor transplantation will be included in this study as they have been in all our previous studies. As in our previous studies, we will use molecular typing (DNA sequencing) of 10 relevant HLA alleles (A, B, C, DR, DQ) for determining donor/recipient matching.

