APPENDIX A: Treatment plan

Day	Clonazepam	Fludarabine	Busulfan	Bu pharmacokinetics	Campath
Test Dose					
-	PO				
-	PO		0.5 mg/kg	x 6	
-	PO				
Treatment Doses					
-7 PO		25 mg/m ²			20 mg
-6	PO	25 mg/m ²	AUC based	x 5	20 mg
-5	PO	25 mg/m ²	AUC based		20 mg
-4	PO	25 mg/m ²	AUC based	(x 5*)	20 mg
-3	PO	25 mg/m ²	AUC based	x 5*	20 mg
-2	PO				
-1					
0					

Comments:

Busulfan administration has been associated with a low incidence of seizures and dilantin is routinely used for seizure prophylaxis. Dilantin use is discouraged in this protocol because exposure to dilantin can affect Busulfan metabolism.⁶⁹

We recommend benzodiazepines e.g clonazepam (klonopin ®) 1 mg PO TID

Scheduling:

Busulfan test dose:

The test dose can be scheduled any day within 8 days prior to admission. Clonazepam will be started with an evening dose, the day prior to the test dose and two doses one day after test dose. Busulfan test-dose will be based on actual body weight and will be accompanied by extensive pharmacokinetic studies. This dose will be given as an outpatient.

Patients will be admitted in the evening of day -8, to start fludarabine on day -7

Fludarabine:

Fludarabine dosing will be based on actual body weight. Fludarabine will be infused over 30 minutes before busulfan treatment dose.

Busulfan treatment doses:

On each day of treatment, busulfan will be administered through a fresh infusion line at a steady rate over 3 hours. Infusion will start in the morning around 8 AM and will be completed around 11 AM, allowing ample time for pharmacokinetic sampling in the afternoon.

*Pharmacokinetic studies will be performed on the day 1 dose and again on the day 4 dose. For logistical reasons (week-end, holidays), day 3 pharmacokinetics may be performed instead of day 4.

Campath

All patients will receive premedication for Campath as per current standards at the UC transplant unit.

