18.1.3 GVHD prophylaxis

Tacrolimus 0.03 mg/kg/day IV CI over 24 hr from 4 PM day -2 until engraftment or when patient is able to take PO, then tacrolimus 0.09 mg/kg PO in 2 divided doses. Tacrolimus should be given at full dose to maintain levels of 5-15 ng/mL through day 100. Thereafter tacrolimus will be tapered by 20% every week unless the patient has developed GVHD.

18.1.4 Supportive care:

Infection prophylaxis and supportive care will be as BMT unit policy. No routine growth factor support will be administered. Growth factor support will be considered in case of delayed engraftment (ANC < $0.5 \times 10^9/L$ on day 12)

18.1.5 Back-up bone marrow harvest (only for recipients of mismatched or unrelated donor transplants)

For patients transplanted in remission, a backup bone marrow or peripheral blood stem cell collection will be considered within two weeks prior to hospital admission as long as the overall marrow cellularity is greater than 30%. All backup harvests will be cryopreserved after processing for buffy coat without any further manipulation. The backup stem cells will be given if deemed clinically necessary in the event of failure to engraft by day +35, graft rejection after day +35, or graft failure after day +35.

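### Appendix A 18.1.3 tapers tacrolimus after day 100 for every recipient, while 9.1.5 continues it until day 180 after mismatched or unrelated donor transplants, and nothing says which text prevails

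*Combined protocol and SAP*

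**What the plan says.** Section 9.1.5 sets the tacrolimus schedule: full dose through day 100 at a target level of 5-15 ng/mL, then a 20% weekly taper unless GVHD has developed. It then makes an exception by donor type: "In recipients of mismatched or unrelated donor transplants, tacrolimus will be continued until day 180". The same 20% weekly taper, with the same GVHD condition, follows that later date.

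Appendix A 18.1.3 gives the same dosing, the same target level and the same general rule: "through day 100. Thereafter tacrolimus will be tapered by 20% every week unless the patient has developed GVHD". It ends there, and 18.1.4 on supportive care follows. It has no day-180 sentence and no reference to donor type.

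Both places present themselves as the treatment plan. The body section is headed "9.0 TREATMENT PLAN" and the appendix "APPENDIX A: Treatment plan". The Treatment Plan entry in the protocol abstract reads only "See appendix A".

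The patients concerned are eligible. The abstract's eligibility list allows "Matched sibling donor, 1 Antigen mismatched relative or matched unrelated donor", and section 5.4 says "Recipients of unrelated donor transplantation will be included in this study as they have been in all our previous studies".

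**The concern.** For one defined group of patients the protocol gives two instructions that cannot both be followed. The group is the one that 9.1.5 singles out for longer prophylaxis. A clinician who goes from the abstract to Appendix A finds a complete-looking tacrolimus rule, with nothing to suggest that an exception stands elsewhere. Following it would mean starting to withdraw GVHD prophylaxis well before 9.1.5 allows.

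The protocol treats this area as important. Section 5.1 lists the type of GVHD prophylaxis among the determinants of transplant outcome, and section 5.2 links treatment-related mortality to how well GVHD is prevented. The disputed interval also falls inside the observation periods for one-year disease-free survival (DFS) and for the 18-month stopping guideline on high-risk extensive chronic GVHD (section 14.0). Section 14.0 pools related and unrelated donor recipients in all analyses. These are statements about timing and relevance. They do not show that either endpoint would move.

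**Working it through.** The plan gives no figure to reproduce. The check compares the two texts and then works out the dates.

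**1. The two rules side by side**

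| Recipient, no GVHD at day 100 | Section 9.1.5 | Appendix A 18.1.3 |
|---|---|---|
| Matched sibling donor | Taper after day 100 | Taper after day 100 |
| Mismatched or unrelated donor | Continue until day 180, then taper | Taper after day 100 |

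The texts agree in the first row and conflict in the second.

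**2. Could 18.1.3 be meant for matched siblings only?** No. Appendix A 18.1.5 is headed "Back-up bone marrow harvest (only for recipients of mismatched or unrelated donor transplants", so the appendix covers the other donor types and separates them where it intends a different rule. In 18.1.3 it does not.

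**3. Does another section settle it?** The tacrolimus drug information in 6.1 gives no post-transplant duration that would decide the point. No sentence ranks section 9 against Appendix A. The abstract's pointer leads to the version without the exception, but it is not a precedence rule.

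**4. Size of the gap**

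- Earliest taper start under 18.1.3: 100 + 1 = day 101.
- Earliest taper start under 9.1.5: 180 + 1 = day 181.
- Difference: 181 − 101 = 80 days. If *until* excludes day 180, it is 180 − 101 = 79 days.

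**5. What the gap means for dose.** The protocol does not say whether each 20% step is taken from the original or the current dose, nor whether the first step falls at the start or the end of the first week. Both are treated as assumptions, with the first step between day 101 and day 107.

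- 20% of the original dose: five steps reach zero, the last one 4 × 7 = 28 days after the first. Under 18.1.3 tacrolimus ends between 101 + 28 = day 129 and 107 + 28 = day 135.
- 20% of the current dose: 11 to 12 steps have been taken by day 180, leaving 0.8^11 = 8.6% to 0.8^12 = 6.9% of full dose.

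Under 9.1.5 the same patient has not begun to taper at day 180.

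**6. Position against the study windows**

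- DFS is counted from the start of therapy (section 14.0). Taking that start as day −7 (first fludarabine) or as early as day −16 (test dose up to 8 days before admission on day −8, section 9.1.2), day 181 falls 181 + 7 = 188 to 181 + 16 = 197 days in, inside 365.
- The 18-month GVHD window, about 1.5 × 365 = 548 days, also contains the interval.
- The 21-day and 60-day dose-limiting toxicity windows in section 14.0 close before day 100, so dose finding is untouched.

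**The case against.** The strongest reply is that this is an omission in an outdated copy, and that the two texts are not rival donor-specific rules. Appendix A differs from section 9 in other places. It starts the busulfan infusion around 8 AM where 9.1.2 says 5 AM. It describes an up-and-down escalation design where 9.1.3 uses the modified continual reassessment method. It also lacks the sentence in 9.1.2 that allows dose adjustment after the first treatment dose. The contents list calls the appendix a treatment scheme, which suggests a summary. A reader holding both texts would normally apply the specific sentence over the general one. Review at least monthly after discharge (15.1) makes it less likely that the study team would overlook 9.1.5. No effect on an endpoint has been shown.

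Much of this stands. Section 9.1.5 is probably the rule intended, and no endpoint effect is claimed here. It is also fair that the tacrolimus gap is one sign of a wider failure to keep Appendix A in step with section 9. But an outdated copy explains the conflict without removing it. The argument from specificity helps only a reader who has both texts in view, and the abstract sends the reader to the incomplete one. Regular visits do not tell the clinician which schedule to follow.

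**Conclusion.** The concern holds. Sections 9.1.5 and 18.1.3 give incompatible tacrolimus schedules for mismatched or unrelated donor recipients who have no GVHD at day 100, and the documents do not say which prevails. The taper starts 80 days apart, or 79 on the narrower reading of *until*. The residual-dose figures depend on the assumed taper base and day of first step; the 80-day gap does not.

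The number of patients affected cannot be stated, because the documents give no donor mix for this trial. Section 5.4 says that seventy percent of patients who might benefit lack a suitably matched related donor, but that is general background. The effect on GVHD or DFS cannot be sized. That 9.1.5 is the current text is an inference from the other differences. This is an error in an operative treatment rule, with a possible safety consequence for a defined group. It does not affect the sample size, the error rates or the dose-finding design.

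**What to change.** Either copy the day-180 sentence and the taper sentence after it from 9.1.5 into Appendix A 18.1.3, or add one sentence stating that section 9 prevails over Appendix A. The precedence sentence, or replacing Appendix A with the current section 9 text, is the better choice because it also covers the infusion-time and escalation-design differences. If only the two sentences are copied, those differences remain. The investigators should confirm that day 180 is the intended date.

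The cost is one or two sentences in a protocol amendment. Sample size, data collection and analysis stay as they are.
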